## DESCRIPTION OF RESEARCH PROJECT

**I – Title of the project:** Evaluation of the effects of osteoperforation and piezocorticism on canine retraction: Randomized controlled clinical trial.

### II - Introduction

Within the field of dentistry, orthodontic treatments are often disregarded or disliked due to their long duration and the negative impact they can have on the patient's physical appearance. Treatment duration can be significantly affected by some procedures, such as canine retractions and the intrusion of teeth. Consequently, this can have a considerable negative impact on patient motivation and can cause or increase the risk of certain side effects associated with the orthodontic treatment, such as root resorption. To address this issue, several procedures have been developed to increase the rate of tooth movement during orthodontic treatment. These accelerated orthodontic procedures have been studied for more than a century. In 1892, surgeons would perform osteotomies around teeth to move the bone segment as a block. Subsequent developments were attributed to Köle during the 1950s, when he introduced a procedure combining the elevation of a mucoperiosteal flap with incisions limited to the cortical bone without entering the medullary space. It was subsequently discovered that corticotomies alone were sufficient to induce an acceleration of teeth movement via a process called Regional Acceleratory Phenomenon (RAP) described a few years earlier by an orthopedist named Frost. The RAP induces a remodeling process of the bone, in addition to a transient state of osteopenia. Studies have shown that the rate of dental movement can be as much as two times faster with the RAP. Its duration of effect was reported to last for four months but is still unproven.

Lately, the research interest has turned towards minimally invasive techniques such as osteoperforation and piezocorticism. These techniques do not require the elevation of a mucoperiosteal flap to induce the RAP, thus reducing the associated comorbidities (discomfort, swelling, hematoma). Osteoperforation has the advantage of being significantly more conservative on the soft and hard tissues since it only consists in making small perforations in the buccal gingiva and cortical bone. On the other hand, piezocorticism has the benefit of allowing hard or soft tissue grafting by a tunnelling technique, if necessary. The efficiency of piezocorticism is well documented and shows a significant acceleration of dental movement. Furthermore, one study suggested that the vibrations emitted by the knife induce a greater acceleration of tooth movement than traditional corticotomies with rotary instruments. A systematic review comparing both techniques revealed that only one controlled human study was conducted so far to determine the efficiency of osteoperforations. This study showed a significant acceleration of tooth movement (2-3X) as well as an increase of inflammatory markers in the gingival crevicular fluid analysis. Studies conducted on rat subjects also report an increase in the rate of tooth movement over a period of two weeks. Thus, the current research will bear an important role in the literature and will demonstrate which technique, osteoperforation or piezocorticism, is the most efficient in increasing the rate of canine retraction while conserving posterior anchorage.

### III – Specific objectives and research hypothesis

**Primary objective:** Compare the rate of canine retraction following the osteoperforation and piezocorticism procedures.

**Secondary objectives:**

- Compare the second order movement of the canine (tipping) between the osteoperforation and piezocorticism procedures.
- Compare the amount of root resorption associated with the osteoperforation and piezocorticism procedures.
- Compare the inflammation process between the experimental and the control group by measuring the inflammatory markers in the gingival crevicular fluid.
- Evaluation of the loss of posterior anchorage by measures on the cone beam computed tomography (CBCT) 3-dimensional radiograph and on the casts.
- Evaluation of the pain level and the impact on quality of life following each procedure using the questionnaire of the visual analogue scale (VAS) of pain.

**Research hypothesis:**

- Primary :
  - o The rate of canine retraction will be faster following the piezocorticisions than the osteoperforations.
- Secondary :
  - o There will be less tipping of the canine following the piezocorticisions than the osteoperforations.
  - o There will be less root resorption following the piezocorticisions than the osteoperforations.
  - o The increase in inflammation will be greater following the piezocorticisions than the osteoperforations.
  - o The posterior loss of anchorage will be less following the piezocorticisions than the osteoperforations.
  - o The pain level and the impact on quality of life will be greater following the piezocorticisions than the osteoperforations.

**Null hypothesis:** The rate of canine retraction is the same following the piezocorticisions, the osteoperforations and without any surgical procedure.

### IV – Experimental design, data acquisition and analysis methodology

**a) Type of research:** Prospective randomized controlled clinical trial.

**b) Characteristics of participants :**

*Sample size :*

- Sample size: 15 patients for the control group and 15 patients for the experimental group. A sample size of 10 subjects has a power of 80% to show a difference between the speed of retraction of the piezocorticism  $1.0 \pm 0.2/12$  weeks and the osteoperforation  $0.8 \pm 0.2\text{mm}/12$  weeks, thus a speed 20% higher for the piezocorticism, with a bilateral alpha of 0.05 and a paired sample T-test. A sample size of 15 also allows to show a difference between the experimental and control group (speed of  $0.5 \pm 0.2\text{mm}/12$  weeks), with a power of more than 80% based on an independent-sample T-test. We will recruit 15 subjects per group to compensate for the possible attrition. The sample will be 50% male, 50% female.

- Experimental group: Bilateral maxillary canine retraction after first premolar extraction with piezocorticision procedure on one side and osteoperforation on contralateral side using a split mouth design.

- Control group: Bilateral maxillary canine retraction after first premolar extraction without any surgical procedures.

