- Collection of gingival crevicular fluid samples on the distobuccal corner of the canine at 0,1, 3, 8 weeks and at the end of treatment to analyze the concentration of cytokines, IL-1, RANKL, OPG and the RANKL/OPG ratio.
- The amount of tooth movement will be measured on the digital dental casts from the tip of the canine to the third rugae palatinae.
- The amount of anchorage loss will be measured on the CBCT using the distance from the nasopalatine foramen to the projection of the mesiobuccal cusp of the first molar on the palatal suture.

**d) Measures and variables:** The rate of canine retraction (mm/12 weeks), the amount of tipping, the amount of root resorption, the amount of posterior loss of anchorage, the level of inflammation and the level of pain.

**e) Statistical analysis:** The Shapiro-Wilk test will be used to determine if the data follows the normal distribution law. A paired sample T-test and the Wilcoxon test will be used to compare the piezocorticision and the osteoperforation within the same subject for the speed of retraction, the amount of tipping, the amount of root resorption and the posterior loss of anchorage. A mixed model analysis for repeated measures (Brunner-Langer method) will be used to compare the evolution of the level of pain and the level of inflammation between the two groups through time.

**V- Expected results:** We are expecting a marked increase in the rate of canine retraction with the piezocorticision and osteoperforation procedures (two times faster than the control group). The canine retraction will be faster on the piezocorticision side than the osteoperforation side. Finally, we are expecting a more noticeable reduction in the root resorption, tipping movement and in the loss of posterior anchorage in the piezocorticision side than the osteoperforation side.

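### Does the expectation that both procedures run at two times the control rate undercut the 0.2 mm difference behind the primary sample size?

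*Protocol*

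**What the plan says.** The primary objective (Protocol, section III) is to compare the canine retraction rate after the two procedures, applied to opposite sides of the same mouth. The primary hypothesis in that section is that piezocorticision gives the faster rate.

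Section IV b (Sample size) plans on these mean rates, each with SD 0.2:

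- piezocorticision: 1.0 per 12 weeks
- osteoperforation: 0.8 mm per 12 weeks
- control: 0.5 mm per 12 weeks

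The power claim begins "A sample size of 10 subjects has a power of 80% to show a difference between the speed of retraction of the piezocorticism". After the two rates it puts the gap in relative terms and names the test: "thus a speed 20% higher for the piezocorticism, with a bilateral alpha of 0.05 and a paired sample T-test". Fifteen patients per group are to be recruited to allow for attrition. The same paragraph claims more than 80% power for experimental against control.

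Section V (Expected results) anticipates a marked increase in the "rate of canine retraction with the piezocorticision and osteoperforation procedures (two times faster than the control group"). Its next sentence reads: "The canine retraction will be faster on the piezocorticision side than the osteoperforation side".

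The Introduction (section II) says of the one controlled human study of osteoperforation that it mentions: "This study showed a significant acceleration of tooth movement (2-3X"). It also describes a doubling of the rate of movement as the upper end of what the regional acceleratory phenomenon has been shown to produce.

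**The concern.** The 0.2 mm gap between the procedures is the whole basis for 10 completers in the primary comparison. It exists because osteoperforation is set at 1.6 times control while piezocorticision is set at 2.0 times. Section V attaches one figure, two times, to both. With control at 0.5, two times is 1.0, which is already the planned piezocorticision rate, so on a literal reading the target difference is zero. The 2-3X cited for osteoperforation in the Introduction points the same way. Nor is a low osteoperforation rate a cautious choice here, because it widens the difference to be detected. If osteoperforation really ran close to twice control with the other two rates unchanged, 15 patients would be far too few. The wrong percentage in the same sentence adds to the impression that the planning figures were not checked against each other.

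**Working it through.** **Inputs.** From section IV b: rates 0.5, 0.8 and 1.0 mm per 12 weeks; SD 0.2 in each; two-sided alpha 0.05; paired t-test with n = 10; 15 recruited per group. From section V: one multiple of two for both procedures. Not stated: the SD of the within-patient difference. I assume 0.20, which corresponds to a correlation of 0.5 between sides when each side has SD 0.2: 0.2 × √(2 × (1 − 0.5)) = 0.20.

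**1. The plan's own figure.** Paired t-test, noncentral t distribution, noncentrality = (difference / SD of difference) × √n.

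- n = 10: (0.2 / 0.20) × √10 = 3.16 on 9 df; power 80.3%. This reproduces the stated 80%, and 10 is the smallest n that reaches it.
- n = 15: (0.2 / 0.20) × √15 = 3.87 on 14 df; power 94.9%.

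The result depends on the assumed correlation:

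| Correlation | SD of difference | Power, n = 10 | Power, n = 15 |
|---|---|---|---|
| 0 | 0.283 | 51.4% | 72.2% |
| 0.25 | 0.245 | 63.4% | 83.6% |
| 0.5 | 0.200 | 80.3% | 94.9% |
| 0.75 | 0.141 | 97.7% | 99.9% |

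**2. Experimental against control.** Independent-sample t-test, 15 per group, 0.8 against 0.5: noncentrality 0.3 / (0.2 × √(2/15)) = 4.11 on 28 df; power 97.7%. For 1.0 against 0.5 it is above 99.9%. The claim of more than 80% holds.

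**3. Ratios to control.** 0.8 / 0.5 = 1.6; 1.0 / 0.5 = 2.0; mean of the two sides 0.9 / 0.5 = 1.8. Section V says two for both.

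**4. The percentage.** 1.0 / 0.8 = 1.25, so piezocorticision is 25% higher. The 20% is the shortfall of 0.8 from 1.0: (1.0 − 0.8) / 1.0. The test works on the 0.2 mm difference, so the percentage does not enter the power.

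**5. What two times could mean.**

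- Exact for each side, control 0.5: both rates are 1.0, the difference is 0, and the rejection probability is 5% at any n. The next sentence of section V and the primary hypothesis both exclude this.
- Average of the two sides, 0.2 gap kept (0.9 and 1.1): power is unchanged at 80.3% and 94.9%.
- Lower control rate (0.4, with 0.8 and 1.0): ratios 2.0 and 2.5; the gap and the primary power are again unchanged.
- Rounded summary of 1.6 and 2.0: the rates in section IV b stand as written.

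**6. What would be lost if only osteoperforation moved up** (control 0.5 and piezocorticision 1.0 held, SD of difference 0.20):

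| Osteoperforation | Gap, mm | Power, n = 10 | Power, n = 15 | n for 80% |
|---|---|---|---|---|
| 1.6 × control | 0.20 | 80% | 95% | 10 |
| 1.7 × control | 0.15 | 56% | 77% | 16 |
| 1.8 × control | 0.10 | 29% | 44% | 34 |
| 1.9 × control | 0.05 | 11% | 15% | 128 |

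Only the first row uses the protocol's rates. The others are sensitivity scenarios.

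**The case for a change.** The best case for a change is that the text gives one multiple for both procedures with no qualifier such as roughly, at most or on average. On a strict reading, two times for both, piezocorticision faster, control 0.5 and piezocorticision 1.0 cannot all be true. The readings that rescue the gap by using 0.9 and 1.1, or a control rate of 0.4, do so by altering figures in section IV b. No source is cited for any of the three rates, and a modest rise in the osteoperforation rate costs a great deal of power.

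Part of this stands. The wording is loose, the percentage is wrong, and the SD behind the 80% is not recorded. It does not show that a planning rate is wrong. Section V is a narrative statement of expectations, not a design input, and it says itself that the sides will differ. A two-fold ceiling, as the Introduction describes it, sits comfortably with 2.0 for the procedure expected to be faster and 1.6 for the other. The 2-3X comes from one cited study whose control rate and measurement interval the protocol does not give, so planning below it is a judgement and not a contradiction. The loss of power in the last table is what any trial shows when its assumed effect is reduced; it is not evidence of an error.

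**Conclusion.** The mismatch is real but small, and it does not reach the design. Section IV b implies 1.6 and 2.0 times control where section V says two times for both, and 25% is written as 20%. The claim that no difference remains to be detected fails, because the protocol says twice that piezocorticision is the faster procedure. The primary power statement rests on the rates in section IV b alone and reproduces at 80.3% for 10 patients, with 94.9% if all 15 complete. This depends on an SD of the within-patient difference of 0.20, my assumption, chosen because it returns the stated figure. With uncorrelated sides, power at 15 would be 72.2%; that sensitivity concerns the unstated SD and has nothing to do with section V. Giving a multiple for each procedure, correcting the percentage or writing down the SD would tidy the text, but would not alter the sample size, the analysis or how the result is read. No change to the plan follows.

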**Inclusion criteria:**

- Dental and/or skeletal Cl I and II requiring maxillary first premolar extraction.
- Young adults 16 years and older.
- Good overall health.
- Complete adult dentition.
- Cooperative.
- Acceptable hygiene.
- Absence of any periodontal disease (gingivitis, periodontitis).

**Exclusion criteria:**

- Non-cooperative, fearful patients or patients with intellectual disability.
- Patients requiring the regular use of nonsteroidal anti-inflammatory drugs (NSAID).
- Use of antibiotics in the last 6 months.
- Previous or current use of bisphosphonates, corticosteroids or immunosuppressive drugs.
- Smokers.
- Patients suffering from uncontrolled systemic diseases (ex. diabetes type I and II).
- Presence of oral or maxillofacial malformations (ex. cleft palate) or dental pathologies (ex. ankylosis, abscess).

**Recruitment modalities:** Patient selection and recruitment will take place at the Graduate orthodontics clinic of the “Université de Montréal”.

**c) Materials and methods**

**Materials**

- CBCT machine
- Piezotome (Piezosurgery®) to perform the piezocorticision procedure.
- Osteoperforation tool (Propel Excellerator; Propel Orthodontics)
- SPEED™ self ligating orthodontic brackets (Strite Industries Limited) + Nickel-Titanium (Ni-Ti) closed coil spring, medium force (150g) (Medium Sentalloy; GAC International Inc).
- Orthodontic force gauge. (Dynamometer).
- Visual analogue scale of pain questionnaire.
- Periotron 8010 and PerioCol paper strips (Oraflow Inc).

**Methods**

- Submission of research proposal for ethics approval.
- Recruitment of patients according to inclusion and exclusion criteria and procurement of informed consent.
- Group randomization using randomized block design.
- Pre-treatment periodontal screening consisting of a 6-point probing around each tooth, measuring of the depth of sulcus and of the distance between the marginal gingiva and the cementoenamel junction.
- Pre-treatment panoramic and cephalometric X-ray, dental impressions, intraoral and extraoral picture and elaboration of treatment plan.
- Bonding of maxillary and mandibular orthodontic brackets and initial alignment and levelling of arches.
- Surgical guide fabrication.
- Pre-retraction CBCT.
- First premolar extraction with patient's general dentist.
- Piezocorticision or osteoperforation one week following premolar extraction.
  - Preoperative rinsing with Chlorhexidine 0.12% (Peridex™) 15 mL for 60 seconds.
  - Topical anesthesia using Benzocaine 20% for 2 minutes.
  - Buccal infiltration of the maxillary canine with lidocaine, epinephrine 1 :100 000 (1,8 mL)
  - For the piezocorticision procedure ([name]): Using the surgical guide, vertical incisions are performed on the buccal mucosa, mesial and distal to the canine, starting 2 mm below the interdental papilla followed by piezocorticision cuts 3 mm deep, extending to the apex of the tooth.
  - For the osteoperforation procedure ([name]): Using the surgical guide, four osteoperforations are performed mesial and distal to the canine along the root. All perforations are 3 mm apart and 5 mm deep.
  - Prescription: Acetaminophen 500 mg q6h PRN if pain and chlorhexidine mouthwash 0.12%, 2X/day X14 days.
- Canine retraction on 0.018 X 0.025 stainless steel (SS) wire using a medium force Ni-Ti closed coil spring with force application from the canine to the molar(s), delivering a force of 150g measured with a gauge.
- Follow up every two weeks for adjustment of forces with the gauge and digital impressions.
- When the canine has reached the desired position, the post-retraction CBCT is taken.
- Evaluation of the pain level of both experimental sides and of the control group using the questionnaire of the VAS immediately after the premolar extraction, then each day for 7 days following the surgeries and the first day after each adjustment of the spring.
- Collection of gingival crevicular fluid samples on the distobuccal corner of the canine at 0,1, 3, 8 weeks and at the end of treatment to analyze the concentration of cytokines, IL-1, RANKL, OPG and the RANKL/OPG ratio.
- The amount of tooth movement will be measured on the digital dental casts from the tip of the canine to the third rugae palatinae.
- The amount of anchorage loss will be measured on the CBCT using the distance from the nasopalatine foramen to the projection of the mesiobuccal cusp of the first molar on the palatal suture.

**d) Measures and variables:** The rate of canine retraction (mm/12 weeks), the amount of tipping, the amount of root resorption, the amount of posterior loss of anchorage, the level of inflammation and the level of pain.

**e) Statistical analysis:** The Shapiro-Wilk test will be used to determine if the data follows the normal distribution law. A paired sample T-test and the Wilcoxon test will be used to compare the piezocorticision and the osteoperforation within the same subject for the speed of retraction, the amount of tipping, the amount of root resorption and the posterior loss of anchorage. A mixed model analysis for repeated measures (Brunner-Langer method) will be used to compare the evolution of the level of pain and the level of inflammation between the two groups through time.

**V- Expected results:** We are expecting a marked increase in the rate of canine retraction with the piezocorticision and osteoperforation procedures (two times faster than the control group). The canine retraction will be faster on the piezocorticision side than the osteoperforation side. Finally, we are expecting a more noticeable reduction in the root resorption, tipping movement and in the loss of posterior anchorage in the piezocorticision side than the osteoperforation side.

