## VI- Schedule

Research protocol: May 2017.

Literature review: July 2017.

Scientific committee: August 2017.

Ethics committee: December 2017.

Recruitment of patients: December 2017 to January 2018.

Data collection: January 2018 to December 2018.

Redaction of the memoir: January to July 2019.

**VII – Limitations of the research:** Firstly, we will only be evaluating the efficiency of the piezocorticision and osteoperforation procedures in the specific and localized case of canine retraction. Hence, these results cannot directly be extrapolated to all types of orthodontic treatments. Secondly, the concomitant extraction of the first premolar will be contributing to the overall RAP phenomenon and thus, could confuse the analysis of our results and exaggerate the amount of reported inflammation. Finally, it is possible that we will not be able to compare the inflammatory effects of the osteoperforation and piezocorticision due to the dynamic nature of the gingival crevicular fluid and the physical proximity of both experimental sites. Still, this information will be valuable to better understand the effect of these approaches on the biological response.

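### No pain score is taken just before surgery, so each procedure's pain level includes any residual extraction pain, and the comparisons lose precision and a check on imbalance

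*Protocol*

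**What the plan says.** The secondary objectives (section III) include "Evaluation of the pain level and the impact on quality of life following each procedure". The matching hypothesis is that pain will be greater with piezocorticision than with osteoperforation.

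The Methods list (IV c) says who is scored: "Evaluation of the pain level of both experimental sides and of the control group using the questionnaire of the VAS". It gives the times as "immediately after the premolar extraction, then each day for 7 days following the surgeries and the first day after each adjustment of the spring". It places the surgery as follows: "Piezocorticision or osteoperforation one week following premolar extraction".

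The experimental group has "Bilateral maxillary canine retraction after first premolar extraction with piezocorticision procedure on one side and osteoperforation on contralateral side using a split mouth design". The control group has "Bilateral maxillary canine retraction after first premolar extraction without any surgical procedures". Allocation to the groups is described as "Group randomization using randomized block design".

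Section IV e) compares how pain develops over time in the two groups with the Brunner-Langer method. It does not say which time points enter that model. Section VII accepts that "the concomitant extraction of the first premolar will be contributing to the overall RAP phenomenon" and may confuse the results. Inflammation is the only outcome it names there.

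**The concern.** A pain level attributed to a procedure needs a reference point from just before that procedure. Here the single earlier score comes a week before surgery and records the extraction. It cannot show how sore either side was when the surgery began. If the extraction anaesthetic was still working when it was taken (an assumption, since the protocol does not describe the extraction), the score would also sit near the bottom of the scale.

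Three things are at stake:

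- The level reported for each procedure contains any soreness left from the extraction.
- If the two extraction sites of a patient, or the two groups, differ in soreness on the day of surgery, nobody can see this or adjust for it.
- No later analysis plan can repair the gap, because a score that was not collected cannot be recovered. The remedy belongs in the data-collection schedule.

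**Working it through.** The protocol gives no pain figure to reproduce. Its power statements concern retraction speed and do not bear on this point. The check sets the schedule against the design, then adds two illustrations with assumed values.

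**1. Schedule against design**

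| Event | Experimental group | Control group | Pain score |
|---|---|---|---|
| Premolar extraction | both sides | both sides | one, straight afterwards |
| Just before surgery, one week later | both sides | no surgery | none |
| Seven days after surgery | one procedure per side | start day not defined | daily |
| Day after spring adjustments | yes | yes | one each time |

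**2. What residual extraction pain does to levels and contrasts**

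Let E be the mean residual extraction pain at the time of scoring. Assume, for illustration only, that piezocorticision adds 20 VAS points and osteoperforation adds 12.

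- Piezocorticision level = E + 20
- Osteoperforation level = E + 12
- Control level on matching days = E

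| E | Piezocorticision level | Piezocorticision minus osteoperforation | Piezocorticision minus control |
|---|---|---|---|
| 0 | 20 | 20 − 12 = 8 | 20 − 0 = 20 |
| 10 | 30 | 30 − 22 = 8 | 30 − 10 = 20 |
| 30 | 50 | 50 − 42 = 8 | 50 − 30 = 20 |

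The level moves with E. The contrasts do not, as long as E has the same mean on both sides and in both groups. A simulation on these values with 15 patients per group gave the same answer (contrasts of 7.99 to 8.01 and 19.95 to 20.02).

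**3. When the control contrast fails**

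If controls are scored on other days, their residual pain is E_c and the contrast becomes 20 + E − E_c. With E = 10 and E_c = 30, as could happen if their seven days were counted from the extraction itself, it is 20 + 10 − 30 = 0. The values are assumed. The point is that cancellation depends on matching days.

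**4. What a baseline score could add**

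Let r be the correlation of a pre-surgery score with a later score, with equal variances and a linear model. Residual variance relative to the unadjusted score is 1 − r² with the baseline as covariate, and 2(1 − r) with a change score.

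| r (assumed) | Covariate | Equivalent n for 15 patients | Change score |
|---|---|---|---|
| 0.3 | 0.91 | 15/0.91 = 16.5 | 1.40 |
| 0.5 | 0.75 | 15/0.75 = 20.0 | 1.00 |
| 0.6 | 0.64 | 15/0.64 = 23.4 | 0.80 |

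The covariate reduces variance throughout this range. The unadjusted change score increases it by 40% at r = 0.3 and gains nothing at r = 0.5.

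These gains do not carry over directly to the planned comparisons. In the split-mouth contrast the pairing already removes each patient's general pain level and use of the scale. The relevant r is then the correlation of the side difference before surgery with the side difference after it, which may be lower. The Brunner-Langer method is also rank-based, so the linear formula is only a guide.

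**The case against.** The strongest reply is that the hypothesis is a contrast and the design already handles extraction pain. Each experimental patient has an extraction on both sides. The randomized controls have the same extractions, no surgery, and are scored for pain. Most of this stands. A reader might infer from the missing score that procedure pain cannot be separated from extraction pain at all. The protocol does not support that reading, because an equal mean component drops out of both contrasts.

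The reply has two limits. First, it does not cover the stated objective of a pain level for each procedure. Second, it needs conditions that the protocol leaves open: the seven control days are undefined, and randomization is described for groups without a stated rule for assigning sides. Even with random sides, 15 patients leave room for chance imbalance.

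Three further objections stand:

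- Nothing in the protocol shows how much extraction pain persists at one week.
- A reader might infer that the extraction score is the first point of the analysed series. Section IV e) does not say so, and the choice may lie in an analysis plan that is not shown.
- A pre-surgery score does not remove pain from the spring, because retraction is listed after surgery.

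**Conclusion.** The point holds in a limited form. No pain score is planned between the extraction and the surgery one week later, so the level reported for each procedure includes any residual extraction pain. In the two comparisons the loss is mainly precision and the means to detect or adjust for imbalance. Bias does not follow from the missing score alone. For the control comparison this rests on scoring controls on matching days, which the protocol should state.

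The size is unknown. The variance reductions of 9% to 36% rest on assumed correlations of 0.3 to 0.6, and should not be claimed for the split-mouth contrast or the rank-based analysis. Pain is a secondary outcome and the primary comparison is untouched. The change is still worth making because it is cheap and cannot be made after the data are collected.

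**What to change.** In IV c), Methods:

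- At the surgery visit, before topical and local anaesthesia, collect one VAS score for each side.
- In controls, collect one VAS score for each side at the matching time, one week after extraction, and count their seven daily scores from that visit.

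In IV e):

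- Use the pre-surgery score as a baseline covariate. For the split-mouth contrast, use the difference between the sides. Do not use an unadjusted change score.
- Report the score taken right after extraction descriptively, outside the post-surgery series.

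The cost is one extra VAS item per side at a visit that already takes place for the experimental group, the matching score in controls, and a few sentences in the protocol.

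### The planned rank analysis of crevicular fluid markers makes no use of the week-0 value as a baseline covariate and so gives up precision, by an amount that depends on a correlation the protocol does not give

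*Protocol*

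**What the plan says.** The Methods list in section IV c) of the Protocol schedules crevicular fluid at the canine "at 0,1, 3, 8 weeks and at the end of treatment": one week-0 value and four later ones. Section IV e) then names the analysis: "A mixed model analysis for repeated measures (Brunner-Langer method) will be used to compare the evolution of the level of pain". The same sentence applies this method to a second outcome, namely "the level of inflammation between the two groups through time". It mentions no baseline covariate and does not say in words what part week 0 plays.

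The comparison of inflammation between experimental and control patients is a secondary objective (section III). The trial has "15 patients for the control group and 15 patients for the experimental group". In the experimental group each patient receives one procedure on each side; control patients have bilateral retraction without surgery (section IV b). The Protocol gives no standard deviation, correlation or power for any marker.

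**The concern.** If week 0 precedes the procedures, randomisation makes the expected group difference there zero. As a response level it then does two things. It pulls the group main effect, averaged over all times, toward zero. And it leaves the treatment effect to a group-by-time interaction with several degrees of freedom, built from contrasts that carry the full noise of the week-0 measurement.

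Using each canine's own week-0 value as a covariate avoids both. With 15 patients per group and no power claim for this objective, precision is scarce, and the value is already being collected.

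The gain depends on week 0 being a true baseline. Surgery takes place one week after premolar extraction, and section VII concedes that extraction could inflate the reported inflammation. The schedule does not say where week 0 lies relative to extraction, surgery or spring placement.

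**Working it through.** **The plan's own power figures.** These concern retraction speed, not inflammation. "A sample size of 10 subjects has a power of 80"% reproduces: difference 0.2 and SD of the difference 0.2 (within-patient correlation 0.5) give 80.3% by the paired t-test. With 15 per group, 0.8 against 0.5 with SD 0.2 gives 97.7% by the independent t-test. There is no figure for markers to reproduce.

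**Inputs.**
- From the Protocol: n = 15 per group, and sampling at weeks 0, 1, 3, 8 and end of treatment. Two-sided alpha 0.05 is stated only for the primary comparison and is carried over here.
- Assumed: correlation ρ between any two times of 0.3, 0.5 or 0.7; equal variances (compound symmetry, SD 1); one value per patient per time; normal theory as an approximation to the rank method; effect d = 0.8 SD.

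**Step 1: one later time.** Relative variances are 1 − ρ² (adjusted), 2(1 − ρ) (change from week 0) and 1 (later value alone). Estimating the slope with 30 patients multiplies the adjusted variance by 1 + 1/26 = 1.038.

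| ρ | Adjusted | Change | Reduction vs change (after slope cost) | Reduction vs later value (after slope cost) |
|---|---|---|---|---|
| 0.3 | 0.91 | 1.40 | 35% (33%) | 9% (6%) |
| 0.5 | 0.75 | 1.00 | 25% (22%) | 25% (22%) |
| 0.7 | 0.51 | 0.60 | 15% (12%) | 49% (47%) |

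**Step 2: tests on equal numerator degrees of freedom, weeks 0, 1, 3 and 8.**
- Interaction, F(3, 84): noncentrality = (15/2) × d² × (3/4) / (1 − ρ) = 3.6/(1 − ρ). This is the same whether the effect is constant over the three later weeks or present at week 1 only.
- Week-0-adjusted joint test, F(3, 81), constant effect: noncentrality = (15/2) × 3d² / [(1 − ρ)(1 + 3ρ)] / 1.038.
- The same test, week-1-only effect: noncentrality = (15/2) × d² × [1 − ρ/(1 + 3ρ)] / (1 − ρ) / 1.038.

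| ρ | Interaction: noncentrality, power | Joint, constant effect | Joint, week 1 only |
|---|---|---|---|
| 0.3 | 5.14, 43% | 10.43, 76% | 5.56, 46% |
| 0.5 | 7.20, 58% | 11.09, 79% | 7.40, 59% |
| 0.7 | 12.00, 82% | 14.91, 90% | 11.93, 82% |

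**Step 3: add the end-of-treatment sample, constant effect.** The interaction noncentrality is (15/2) × d² × (4/5) / (1 − ρ) = 5.49, 7.68, 12.80, so power with F(4, 112) is 42/56/81%. For the adjusted joint test it is (15/2) × 4d² / [(1 − ρ)(1 + 4ρ)] / 1.038 = 12.01, 12.33, 16.22, so power with F(4, 108) is 78/80/90%. The picture does not change.

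**Step 4: dilution of the group main effect.** Over weeks 0, 1, 3 and 8 the constant effect averages 0.8 × 3/4 = 0.6 SD with variance (1 + 3ρ)/4. Power is 63/52/44% at ρ = 0.3/0.5/0.7. The week-0-adjusted mean of weeks 1, 3 and 8, also one degree of freedom, has variance [(1 + 2ρ)/3 − ρ²] × 1.038 and power 88/89/96%.

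**The case against.** **The Protocol never says that week 0 is a response level.** A reader might infer that it does. It names a method and a comparison of profiles over time, and a statistical analysis plan not shown could add a baseline term. This stands as a limit on the wording. It does not remove the point, because the method is named rather than deferred and in its usual form has no place for a continuous covariate.

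**Week 0 as a response is not wasteful in itself.** A likelihood model that constrains the groups to a common week-0 mean is about as efficient as covariate adjustment. That is correct. The loss comes from leaving the week-0 group means free, as the named method does in its usual form.

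**A focused average is not a fair comparator for the interaction.** At ρ = 0.5 one could set 58% for the interaction against 89% for the adjusted mean (91% before the slope cost). That mixes three degrees of freedom with one: the unadjusted one-degree-of-freedom change contrast already reaches 74%. The average also suits a constant effect. If the effect exists at week 1 only, which fits the transient response described in the Introduction, the adjusted average has about 19% power and the interaction keeps 58%. This objection stands, and it is why step 2 compares joint tests and why the fix does not rest on an average.

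**A rank method is reasonable** for 15 per group with possibly skewed concentrations and a ratio. This also stands. Nothing in the documents shows that it must give way to a log-normal model, and adjustment can be done on ranks.

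**The stakes are low.** The objective is secondary, and section VII already urges caution with the inflammation data. Agreed.

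**Conclusion.** The point holds as a loss of precision on a secondary objective, not as bias. On the natural reading of section IV e), the week-0 value serves only as a time level, and adjusting for it would do better or about as well at every correlation examined. Like for like, and for a constant 0.8 SD effect, power rises from about 43/58/82% to 76/79/90% at ρ = 0.3/0.5/0.7. For an effect at week 1 only the two tests are about equal.

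A reader might sum this up as a quarter of the information wasted. The documents do not support that figure. It needs ρ = 0.5 at a single later time, and no marker correlation is given; the supported statement is the range in step 1. The direction does not hang on one value of ρ, but the size does. It also rests on compound symmetry, the assumed effect, normal theory standing in for a rank method, and one value per patient per time.

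**What to change.** In section IV e), for each marker:

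- Analyse all samples after week 0 (weeks 1, 3, 8 and end of treatment) by group, week and group-by-week, with the same canine's week-0 value as a covariate, on ranks or on the log scale.
- Test the group effects jointly across weeks.
- Include terms for side or procedure and for patient, because each patient contributes two canines and the experimental group has a different procedure on each side. State which contrast the two groups refers to.
- Keep the Brunner-Langer profile analysis alongside.

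In the sampling schedule in section IV c), state when the week-0 sample is taken relative to surgery and spring placement. The adjustment is valid only if the sample precedes both.

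The cost is wording and one covariate, which inflates the adjusted variance by about 4% (1/26) with 30 patients. No new samples or visits are needed.
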